5.6 Consent – Other Considerations

5.6. 1 Non-English-Speaking Subjects

The study will include Spanish-speaking participants. Staff who speak Spanish fluently will communicate with these subjects during the study procedures. Alternatively, if the preferred language is Spanish, LanguageLine can be utilized for translation.

5.6. 2 Cognitively Impaired Adults

5.6.2.1 Capability of Providing Consent

Not applicable.

5.6.2.2 Adults Unable to Consent

Not applicable.

5.6.2.3 Assent of Adults Unable to Consent

Not applicable.

5.6. 3 Subjects who are not yet adults (infants, children, teenagers)

5.6.3.1 Parental Permission

Not applicable.

5.6.3.2 Assent of subjects who are not yet adults

Not applicable.

6.0 HIPAA Research Authorization and/or Waiver or Alteration of Authorization

6.1 Authorization and/or Waiver or Alteration of Authorization for the Uses and Disclosures of PHI

Check all that apply:

- Not applicable, no identifiable protected health information (PHI) is accessed, used or disclosed in this study. [Mark all parts of sections 6.2 and 6.3 as not applicable]
- Authorization will be obtained and documented as part of the consent process. [If this is the only box checked, mark sections 6.2 and 6.3 as not applicable]
- Partial waiver is requested for recruitment purposes only (Check this box if patients' medical records will be accessed to determine eligibility before consent/authorization has been obtained). [Complete all parts of sections 6.2 and 6.3]
- Full waiver is requested for entire research study (e.g., medical record review studies). [Complete all parts of sections 6.2 and 6.3]
- Alteration is requested to waive requirement for written documentation of authorization (verbal authorization will be obtained). [Complete all parts of sections 6.2 and 6.3]

6.2 Waiver or Alteration of Authorization for the Uses and Disclosures of PHI

6.2. 1 Access, use or disclosure of PHI representing no more than a minimal risk to the privacy of the individual

6.2 .1.1 Plan to protect PHI from improper use or disclosure

Information is included in the “Confidentiality, Privacy, and Data Management” section of this protocol.

6.2 .1.2 Plan to destroy identifiers or a justification for retaining identifiers

Protected health information (PHI) will be used for recruitment through the EMR by members of the study team. All EMR data and study data will be input into REDCap (i.e., insurance status, and date and results of previous Pap/HPV tests). There will be two databases for participant data. The first linking list will contain the medical record number (MRN) and the unique study ID number. This list will be destroyed after data collection. The second linking list will have the study ID with all study data. This second linking list will be kept for up to two years after data collection.

Identifiers will be destroyed after the completion of data analysis.

6.2. 2 Explanation for why the research could not practically be conducted without access to and use of PHI

The proposed study requires enrollment of participants who have abnormal findings on Pap/HPV tests to compare those results with the findings from a self-sampled HPV test. Identification of these participants would be infeasible using other methods.

6.2. 3 Explanation for why the research could not practically be conducted without the waiver or alteration of authorization

Prospective identification of participants with abnormal findings on Pap/HPV tests using PHI prior to consent will be more practical and efficient than obtaining consent prior to determining whether a potential participant had abnormal findings on these tests.

Having participants provide implied consent by using the Summary Explanation of Research is more practical because it allows the study team to send a kit to participants prior to their appointment, and therefore gives the participant more time to complete study procedures. This process also makes it easier to participate in the study since all materials are mailed to the participants home, and they will not take up any extra clinic time during their appointment.

6.3 Waiver or alteration of authorization statements of agreement

Protected health information obtained as part of this research will not be reused or disclosed to any other person or entity, except as required by law, for authorized oversight of the research study, or for other permitted uses and disclosures according to federal regulations.

The research team will collect only information essential to the study and in accord with the 'Minimum Necessary' standard (information reasonably necessary to accomplish the objectives of the research) per federal regulations.

Access to the information will be limited, to the greatest extent possible, within the research team. All disclosures or releases of identifiable information granted under this waiver will be accounted for and documented.

7.0 Study Design and Procedures

7.1 Study Design

After the participant is screened and informs the study team member that they would like to enroll in the study, an HPV self-sampling kit, the instructions on how to use it, a summary explanation of research, PSH lab Pathology Services Special Account Requisition form, and a letter from the principal investigator (PI) (see "[name] Self-sampling Letter") will be mailed to study participants. Participants will be asked to complete the HPV self-sampling kit within a week. 3-5 days before the colposcopy appointment a study team member will reach out to check if study participants have completed their HPV self-sampling kit. Those that have completed the kit will complete a survey (HPVSelSamplingAcceptabilityAn) over the phone and get an appointment reminder. They will mail their HPV self-sampling kit and PSH lab Pathology Services Special Account Requisition form to the lab. On the day of their appointment, their clinician will perform a colposcopy following normal clinical procedures.

Participants who have not completed their HPV self-sampling kit will get instructions not to use the HPV self-sampling kit before the colposcopy and get an appointment reminder. They will then go to their appointment where the clinician will perform the colposcopy. After their visit, the participant will receive a reminder to use the HPV self-sampling kit within two weeks. The participant will receive a maximum of three phone calls after their colposcopy appointment to remind them to return their completed self-sampling kit. Seven days after the colposcopy appointment the research project manager will call the participant to determine if she completed the HPV self-sampling kit and, if so, they will complete a survey (HPVSelSamplingAcceptabilityAn) over the phone. If the participant has not completed the kit or does not respond, a second phone call will then occur 10 days after the colposcopy appointment. A final phone call will up to 21 days after the colposcopy appointment. If the self-sampling kit is not collected 21 days after the colposcopy or if the study team is unable to reach the participant, their participation will be considered incomplete.

Participants must complete the self-sampling kit within 14 days before or after their colposcopy visit, meaning that there is a 28 day window for participants to collect the sample. A 2nd HPV self-sampling kit will only be mailed if the participant states that she lost or did not receive the first one. Participants will receive a maximum of 2 HPV self-sampling kits.

Once the HPV self-sampling kit has been returned and the survey completed, the study participants will be mailed an incentive in the form of a Greenphire ClinCard, and a thank you letter from the PI. Analysis of the self-sampling specimens will be conducted to determine HPV DNA positivity to compare to the results of the previous Pap test, HPV test, and colposcopy. EMR data will be used to check insurance status, and the date and result of Pap test, HPV test, and colposcopy.

7.2 Study Procedures

Survey and HPV self-sampling kit

7.2. 1 Up to 21 days before the colposcopy appointment

A study team member will obtain implied verbal consent from the participants and mail the HPV self-sampling kit with the instructions, a summary explanation of research, PSH lab Pathology Services Special Account Requisition form, and [name] Self-sampling Letter.

7.2. 2 3-5 days before the colposcopy appointment

A study team member will call study participants to provide a reminder to attend their colposcopy appointment and, if they completed their HPV self-sampling kit, take a survey (HPVSelfSamplingAcceptabilityAn) over the phone. Those that did not complete the HPV self-sampling kit will get an appointment reminder and be told not to use the self-sampling kit before the colposcopy.

7.2. 3 Up to 21 days after colposcopy appointment

Seven days after their colposcopy visit, a study team member will call those participants who did not complete the HPV self-sampling kit prior to the colposcopy appointment to complete a survey (HPVSelfSamplingAcceptabilityAn) over the phone. If they still have not completed the HPV self-sampling kit, they will be reminded to complete the self-sampling kit and a study team member will schedule another phone call to complete the survey (HPVSelfSamplingAcceptabilityAn) up to 21 days post-colposcopy. Once the HPV self-sampling kit has been returned and the survey completed, the study team will mail out the participant's incentive and the Thank You Letter. If the participant did not complete the kit then no further contact will be made after day 21, and the participant will not receive a gift card nor will they be included in the goal of 30 total completers.

7.3 Duration of Participation

Participants will be in the study for up to five weeks.

7.4 Test Article(s) (Study Drug(s) and/or Study Device(s))

7.4. 1 Description

The Evalyn® Brush is a self-sampling kit that screens for HPV, a leading cause of cancer death among women. This tool has recently been FDA approved, but has not been incorporated into national clinical guidelines. This product is a small pink capped brush that can be used to take a sample of cervical cells.

7.4. 2 Treatment Regimen

Participants will take a sample of their cervix cells that amounts to a few millimeters of bio specimen.

7.4. 3 Method for Assigning Subject to Treatment Groups

Not applicable

7.4. 4 Subject Compliance Monitoring

Subject compliance will be confirmed once their lab results are received from the PSH lab.

7.4. 5 Blinding of the Test Article

Not applicable

7.4. 6 Receiving, Storage, Dispensing and Return

7.4 .6.1 Receipt of Test Article

1 HPV self-sampling kit will be sent to the PSH lab in a prepaid mailing. Inside the mailing will be the HPV self-sampling kit with the instructions and a PSH lab Pathology Services Special Account Requisition form. The kits will be supplied by the Department of Family and Community Medicine.

7.4 .6.2 Storage

Before HPV self-sampling kits are sent to study participants, they will be stored in a locked cabinet in the Department of Family and Community Medicine offices at [name]. Kits mailed to the lab will be disposed of after analysis.

7.4 .6.3 Preparation and Dispensing

Before it is sent to the participant, the PSH lab Pathology Services Special Account Requisition document will be labeled with the participant's ID #, date of birth, and sex. The Mailing will include the HPV self-sampling kit with the instructions, a summary explanation of research, PSH lab Pathology Services Special Account Requisition form and [name]. Also, the package will include a prepaid and labeled mailing to send the kit and Pathology Services Special Account Requisition document to the PSH lab. Participants will need to include the date and time of sample collection on the Requisition form.

7.4 .6.4 Return or Destruction of the Test Article

HPV self-sampling kits not be returned to participants. The samples will be analyzed and the kits will be destroyed by the PSH lab once analysis is complete.

7.4 .6.5 Prior and Concomitant Therapy

Not applicable

8.0 Subject Numbers and Statistical Plan

8.1 Number of Subjects

We expect to consent and screen no more than 60 women to achieve a final sample size of 30 participants after accounting for potential screen failures.

8.2 Sample size determination

Assuming $p < .05$ and $\beta > 0.80$, we need 30 participants to determine concordance/non-inferiority of test results across the two different methods using a Fisher's exact test and Cohen's kappa coefficient.

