1.0 Objectives

1.1 Study Objectives

The main objective is to compare the test characteristics of the human papillomavirus (HPV) self-sampling kit versus clinician-sampled HPV testing for cervical cancer screening. This study seeks to find out if the HPV self-sampling kit is non-inferior to standard clinician-sampling practices.

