3.0 Inclusion and Exclusion Criteria

3.1 Inclusion Criteria

1. Ages 30-65 years
2. Penn State Health (PSH) patient
3. Female
4. Has an intact cervix
5. With abnormal findings on Pap/HPV test that requires a colposcopy for follow-up
6. Speaks, reads, or writes well in English or Spanish

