8.3 Statistical methods

We will conduct Fisher's exact tests to examine our primary study outcome, i.e., concordance/non-inferiority of HPV self-sampling test results versus clinician-sampled test results. Additional analyses of the concordance across test will use Cohen's kappa coefficient. In addition, we will summarize survey results using descriptive analysis, including calculating means, Pearson's correlation coefficients, and Fisher's exact tests.

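### The claim in 8.2 that 30 women settle non-inferiority is unsupported: Fisher's exact test and kappa do not test a paired difference against a margin, and no margin is stated

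*Combined protocol and SAP*

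**What the plan says.** Section 1.1 sets the question: "This study seeks to find out if the HPV self-sampling kit is non-inferior to standard clinician-sampling practices". Section 8.2 gives the sample size: "Assuming $p < .05$ and $\beta > 0.80$, we need 30 participants to determine concordance/non-inferiority of test results". The same sentence ties that number to two methods, Fisher's test and kappa. Section 8.3 names the primary analysis: "We will conduct Fisher's exact tests to examine our primary study outcome, i.e., concordance/non-inferiority of HPV self-sampling test results versus clinician-sampled test results". It adds kappa as a further analysis of concordance.

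The comparison is within each woman. Section 7.1 has the self-sample tested for "HPV DNA positivity to compare to the results of the previous Pap test, HPV test, and colposcopy". Entry depends on that earlier testing: 3.1 requires a woman "With abnormal findings on Pap/HPV test that requires a colposcopy for follow-up", and 6.2.2 describes "enrollment of participants who have abnormal findings on Pap/HPV tests to compare those results with the findings from a self-sampled HPV test".

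No section states a margin, an expected discordance or difference, a one- or two-sided level, or a null or target kappa. Sections 8.2 and 8.3 read as complete text, with no sign of redaction.

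**The concern.** A non-inferiority question on paired binary results asks whether self-sampling positivity falls below clinician-sampled positivity by less than a set amount. The two named methods answer other questions. Fisher's test on the paired table asks whether the two results are associated. Kappa uses the pairing, but it summarises agreement beyond chance.

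The entry rule makes Fisher's test fit less well still. Women enter because of an abnormal earlier result, and the self-sample is compared with that earlier testing. There may be few clinician HPV-negative women, and discordance may run mainly toward self-negative/clinician-positive.

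If the plan is followed as written, the primary p-value can be small when self-sampling misses many positives and large when nearly all pairs agree. Section 8.2 would lend either result the standing of an adequately powered answer.

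**Working it through.** **1. Can 30 be reproduced?** The stated inputs are p < .05, 0.80 (read as power) and 30 completers (8.1, 8.2). They are not enough. Values from outside the documents that land near 30 are:

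- Test of kappa = 0, standard error 1/√n, 80% power: kappa = (z_α + z_β)/√30. Two-sided: (1.960 + 0.842)/5.477 = 0.51. One-sided: (1.645 + 0.842)/5.477 = 0.45.
- Paired non-inferiority, true difference 0, n = discordance × (z_α + z_β)²/margin². With 15% discordance, a 20-point margin and one-sided 0.025: 0.15 × 7.849/0.04 = 29.4, so 30. With 5%, 10 points and one-sided 0.05: 0.05 × 6.183/0.01 = 30.9, so 31. These are normal approximations; exact score-test power at n = 30 is 68% and 53% for these two cases.

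Several unrelated assumptions give about 30, and the documents state none of them.

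**2. What does Fisher's test do with 30 pairs?** The tables are illustrative, because the number of clinician HPV-negatives is not in the documents. Cells are ordered both positive / self-positive only / clinician-positive only / both negative.

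| Table | Meaning | Fisher p (two-sided) | Kappa |
|---|---|---|---|
| 15/0/0/15 | perfect agreement | 1.3e-8 | 1.00 |
| 0/15/15/0 | perfect disagreement | 1.3e-8 | -1.00 |
| 10/0/10/10 | 10 of 20 clinician positives missed | 0.011 | 0.40 |
| 27/1/2/0 | 27 of 30 pairs agree | 1.0 | -0.05 |
| 27/0/3/0 | no clinician-negatives, 3 missed | 1.0 | 0 |
| 10/0/20/0 | no clinician-negatives, 20 missed | 1.0 | 0 |

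The first two p-values are equal because each is 2/C(30,15) = 2/155,117,520. With no clinician-negative woman, only one table fits the margins, so p = 1.0 whatever self-sampling finds.

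If 8.3 instead means a method-by-result table with 60 results treated as independent, 30/30 versus 25/30 gives p = 0.052. A loss of 5/30, or 17 points, would then be non-significant. That reading ignores the pairing and also has no margin.

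**3. What could 30 pairs do with a suitable test?** All outcomes for n = 30 were enumerated with the restricted-maximum-likelihood paired score test. Assumed: true difference 0, discordance 5%/10%/20%.

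| Margin | One-sided 0.05 | One-sided 0.025 |
|---|---|---|
| 10 points | 53% / 39% / 29% | 27% / 24% / 18% |
| 20 points | 98% / 92% / 75% | 90% / 78% / 61% |

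The margin, the discordance and the sidedness together decide whether 30 is enough.

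**4. Notation.** Beta conventionally denotes type II error, and power is 1 - beta. Taken literally, "Assuming $p < .05$ and $\beta > 0.80" would mean power below 20%.

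**The case against.** **Thirty may be the right number.** The 20-point rows in step 3 show inputs at which 30 pairs exceed 80% power. This stands. A reader might infer that 30 is too small, but the documents do not support that, because they fix no margin or discordance against which to judge it. One scenario needs care. At a 10-point margin with 10% discordance all self-negative/clinician-positive, the rejection rate at one-sided 0.05 is 4%. The true difference there equals the margin, so this is type I error and says nothing about lack of power.

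**The plan states no decision rule for Fisher's p.** This is true, and kappa is also planned. A reader might infer that the sponsor would declare non-inferiority from a small or a large p, but 8.3 does not say so. Kappa flags some misleading tables (0.40 when half the positives are missed). It does not help when no woman is clinician-negative: it is 0 with 3 missed and 0 with 20 missed.

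**The tables are invented and some are extreme.** This is also true. Section 3.1 allows entry on Pap or HPV findings, so some women may be clinician HPV-negative or have no clinician HPV result. The tables show what the test can do, not what is likely here.

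**The study is small and minimal risk.** The documents do not call it a pilot, and 8.2 makes a powered claim. A pilot framing would favour the estimation option below.

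**Conclusion.** The point holds as a mismatch between the question and the primary method, together with a powered claim that has no stated basis. It should be corrected before analysis, because 8.3 attaches Fisher's test to the primary outcome and that test cannot separate perfect agreement from perfect disagreement.

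The mismatch rests only on the text of 1.1, 7.1, 8.2 and 8.3. The power figures rest on assumed margins, discordance and sidedness with a true difference of 0. They run from 18% to 98%, and that spread is itself the finding: the adequacy of 30 cannot be judged from the plan. The literal reading of beta as a design with under 20% power is not supported either; it is a labelling slip and minor.

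**What to change.** Keep 30 women and choose one of two options of equal standing.

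**Option A, estimation.**
- In 8.2, delete the power claim and state precision, for example: if all 30 women have a clinician HPV result and 27 pairs agree, the exact 95% CI for agreement is 73.5% to 97.9%; if the 3 discordant pairs split 1 self-positive only and 2 clinician-positive only, the paired difference is (1 - 2)/30 = -3.3 points (95% score CI -18.8 to 11.3); intervals widen if fewer women have a clinician HPV result.
- In 8.3, replace Fisher's test as primary with the paired 2x2 table; overall, positive and negative agreement with exact CIs on the actual denominators; and the paired difference in positivity with a score CI.
- Note there that entry on an earlier abnormal test may push discordance toward self-negative/clinician-positive.
- Keep kappa as supportive, noting that it is 0 or undefined if no woman is clinician-negative.
- Add to 1.1 that the study estimates agreement and will not declare non-inferiority.

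**Option B, keep non-inferiority.**
- In 8.2, state the margin, discordance, true difference, sidedness and paired test at which 30 pairs reach the stated power.
- In 8.3, name that test as primary.

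Under either option, correct the beta notation. The cost is rewriting 8.2 and the first two sentences of 8.3, plus one sentence in 1.1 under Option A. No patients, visits or data are added. The downside is a less favourable claim: non-inferiority is either not declared, or is tied to a margin the sponsor must defend.

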8.3 Statistical methods

We will conduct Fisher's exact tests to examine our primary study outcome, i.e., concordance/non-inferiority of HPV self-sampling test results versus clinician-sampled test results. Additional analyses of the concordance across test will use Cohen's kappa coefficient. In addition, we will summarize survey results using descriptive analysis, including calculating means, Pearson's correlation coefficients, and Fisher's exact tests.

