1.2 Primary Study Endpoints

The primary outcomes of this study are to analyze the screening results on self-sampling kits compared to clinician-collected HPV test, Pap smear results, and colposcopy.

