2.0 Background

2.1 Scientific Background and Gaps

The American Cancer Society estimates that 4,170 women in the United States (US) will die from cervical cancer in 2018.¹ Screening can reduce cancer mortality by (1) detecting malignancies when they are more treatable² and (2) for some tests, identifying precancerous lesions for removal. Guidelines recommend cytology and/or HPV testing for cervical cancer screening among women ages 30-65 years, but screening rates are suboptimal.^{3,4}

To help bridge these gaps in screening, HPV self-sampling would be an alternative to clinical screening. However, there are concerns about the efficacy and comparability of self-sampling kits as an effective tool to detect cervical cancer.

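### Fisher's exact test, the method named for the paired primary outcome, cannot establish agreement or non-inferiority, and kappa covers only part of the gap

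*Combined protocol and SAP*

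**What the plan says.** The aim in section 1.1 is non-inferiority: "This study seeks to find out if the HPV self-sampling kit is non-inferior to standard clinician-sampling practices". Section 1.2 makes three comparisons primary: "analyze the screening results on self-sampling kits compared to clinician-collected HPV test, Pap smear results, and colposcopy". Under section 7.1 the self-samples are tested to "determine HPV DNA positivity to compare to the results of the previous Pap test, HPV test, and colposcopy", so each woman supplies both halves of every comparison.

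For the analysis, section 8.3 states: "We will conduct Fisher's exact tests to examine our primary study outcome, i.e., concordance/non-inferiority of HPV self-sampling test results versus clinician-sampled test results". It then adds: "Additional analyses of the concordance across test will use Cohen's kappa coefficient". Section 8.2 bases the sample size on the same two methods: "we need 30 participants to determine concordance/non-inferiority of test results across the two different methods using a Fisher's exact test", together with Cohen's kappa. It states p below .05 and β above 0.80.

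Section 8.3 does not say which table Fisher's test is applied to, or which p-value would support which conclusion. The document gives no non-inferiority margin, paired test, paired difference, confidence interval or kappa threshold.

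**The concern.** Fisher's test can be applied to these data in two ways, and neither answers section 1.1.

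- **Cross-table of self by clinician result.** The null hypothesis is independence. A small p says the two results are associated. It does not say that they agree, or that few clinician positives are missed. The p-value also depends on how many clinician-negative women were enrolled.
- **Positives out of 30 against positives out of 30.** This treats one group of women as two independent groups and tests for zero difference. A large p is not evidence of non-inferiority.

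The entry rule makes the first reading more fragile. Women are enrolled "With abnormal findings on Pap/HPV test that requires a colposcopy for follow-up", so clinician-negative HPV results may be few. The document does not say how few.

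At stake is the main conclusion. Section 11.2 says that, if findings are similar, self-sampling may become an option for underserved women. A significant Fisher p could be read as that similarity while a substantial share of positives is being missed.

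**Working it through.** **Inputs.** From the document: 30 completers (8.1, 8.2), alpha 0.05 with sidedness not stated, and β above 0.80, read here as 80% power. The document gives no positivity, agreement or discordance rates, so every table below is an assumption. Tables list both positive / clinician-only positive (b) / self-only positive (c) / both negative, with n = 30 pairs.

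**The plan's own figure.** The figure of 30 cannot be derived, because there is no margin, rate or target kappa. The nearest match is a two-sided test of kappa against zero with standard error 1/√n. It has 80% power if true kappa is (1.96 + 0.84)/√30 = 0.51. That tests association beyond chance, not non-inferiority.

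**Step 1: Fisher on the cross-table, with positives missed.** Take 20/7/0/3. There are 27 clinician positives, 3 clinician negatives and 10 self-negatives. With the margins fixed, the probability that all 3 clinician negatives fall among the 10 self-negatives is C(10,3)/C(30,3) = 120/4060 = 0.030. No other table is as improbable, so p = 0.030 whether the test is one- or two-sided. For the same data:

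- positive agreement is 20/27 = 74% (exact 95% CI 54 to 89);
- the paired difference is (c − b)/n = (0 − 7)/30 = −23 points;
- the Tango score interval contains every δ with |c − b − nδ| / √[n(2q + δ(1 − δ))] ≤ 1.96, where q is the fitted clinician-only probability under δ. At δ = −0.409, q = 0.409, and the ratio is (−7 + 12.28)/√7.25 = 1.96. The interval is −41 to −9 points.

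**Step 2: Fisher on the cross-table, with agreement held constant.** Agreement is 27/30 (exact 95% CI 73 to 98) with three missed positives. The paired difference is −10 points (score CI −26 to +2) in every row. Kappa is (observed − expected agreement)/(1 − expected agreement).

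| Table | Clinician-negatives | Fisher p | Kappa |
|---|---|---|---|
| 27/3/0/0 | 0 | 1.0 | 0 |
| 26/3/0/1 | 1 | 4/30 = 0.13 | 0.37 |
| 25/3/0/2 | 2 | 10/435 = 0.023 | 0.53 |
| 24/3/0/3 | 3 | 20/4060 = 0.005 | 0.62 |

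The p-value follows case mix while agreement and the deficit stay the same. Kappa moves as well.

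**Step 3: Fisher on 27/30 against 20/30.** These are the Step 1 data without the pairing. Fisher gives p = 0.057. Exact McNemar on the 7 v 0 discordant pairs gives 2 × (1/2)^7 = 0.016. The unpaired reading hides a deficit that the paired data show.

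**Step 4: what 30 pairs can do for non-inferiority.** Power is by full enumeration of the Tango test at one-sided 0.025, with no true difference.

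| Assumed discordance | Margin 10 points | Margin 15 points | Margin 20 points |
|---|---|---|---|
| 5% | 27% | 66% | 90% |
| 10% | 24% | 53% | 78% |
| 20% | 18% | 37% | 61% |

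**The case against.** The best defence is that kappa is in the plan. It measures agreement, it separates perfect agreement (15/0/0/15, kappa +1) from total disagreement (0/15/15/0, kappa −1), and section 8.2 names it alongside Fisher's test. This stands in part: a reader might infer that concordance is not addressed at all, and that would be wrong. But section 8.3 makes kappa additional, gives it no interval or criterion, and it does not test non-inferiority. At a constant 90% agreement it runs from 0 to 0.62 in Step 2.

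A second defence is that the examples are chosen to embarrass the test. The row with p = 1.0 needs no clinician-negative woman at all. The identical two-sided p = 1.3 × 10⁻⁸ for 15/0/0/15 and 0/15/15/0 disappears if the test is one-sided. Both remarks are fair. They do not touch 20/7/0/3, where p stays at 0.030 one-sided, or the other rows of Step 2.

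A third is that this is a small study meant to support larger efforts (2.2), so a formal non-inferiority analysis is more than it needs. That is a reason to restate the aim. It does not defend a test that cannot deliver the aim as now stated in 1.1, 8.2 and 8.3.

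**Conclusion.** The point holds: following section 8.3 as written, neither a small nor a large Fisher p supports the conclusion that section 1.1 seeks, and nothing elsewhere in the document fills the gap. This follows from the paired design and from what the test examines. The sizes rest on assumed tables of 30 complete pairs and are illustrations, not forecasts.

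Three stronger readings are not supported.

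- A reader might infer that 30 women is the wrong number. The document gives too little to derive 30 or to refute it, and Step 4 depends on assumed margins and discordance.
- A reader might infer that non-inferiority must be dropped. Whether to keep that aim is the sponsor's choice; what is needed is a method that matches it.
- A reader might infer that a paired difference in HPV positivity would settle the objective. Section 1.1 speaks of test characteristics and 1.2 also names Pap and colposcopy. Extra false positives would raise self-sample positivity and help it pass.

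**What to change.** In section 8.3, replace Fisher's test for the primary outcome with:

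- the paired 2×2 table of self by clinician HPV result among women who have both, stating how many do. Entry on an abnormal Pap/HPV finding does not guarantee a clinician HPV result for everyone, since section 2.1 notes that "Guidelines recommend cytology and/or HPV testing for cervical cancer screening among women ages 30-65 years";
- positive agreement and, where estimable, negative agreement, with exact 95% CIs;
- the paired difference in positivity with a score (Tango) or Newcombe paired CI;
- kappa with a CI, and exact McNemar, as supporting analyses;
- for Pap and colposcopy, the corresponding cross-tables with exact CIs, including self-sample positivity among women with and without disease on colposcopy.

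Then choose one of two routes.

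(a) State 1.1, 8.2 and 8.3 as estimation of agreement, and describe the precision that 30 women give, for example 73 to 98% around 27/30.

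(b) Keep non-inferiority. Fix a justified margin before the self-sample results are analysed, conclude non-inferiority only if the lower paired CI bound exceeds minus the margin, and restate the power in 8.2.

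Under either route, replace the 8.2 statement, which rests on Fisher's test and kappa and gives no margin or rates.

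The cost is rewriting three sections, with no extra women or data. The downside is wide intervals and a more modest conclusion. Under (b) the restated power may be low: with 10% discordance and no true difference, it is 24% at a 10-point margin, where about 100 pairs would be needed for 80%.
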